# Proprietary Information of MD Anderson

Protocol # 2016-0251

Date: February 24, 2020

44

21. Is pregnant or breastfeeding, or expecting to conceive or father children within the projected duration of the trial, starting with the screening visit through 120 days after the last dose of trial treatment.
22. Has received prior therapy with an anti-PD-1, anti-PD-L1, or anti-PD-L2 agent or with an agent directed to another stimulatory or co-inhibitory T cell receptor (eg, CTLA-4, OX-40, CD137)..
23. Has severe hypersensitivity ( $\geq$ Grade 3) to pembrolizumab and/or any of its excipients.
24. Has a known history of human immunodeficiency virus (HIV) infection. No HIV testing is required unless mandated by local health authority.
25. Has a known history of active tuberculosis (TB; *Bacillus tuberculosis*).
26. Has received a live vaccine within 30 days prior to the first dose of trial drug. Examples of live vaccines include, but are not limited to, the following: measles, mumps, rubella, varicella/zoster (chicken pox), yellow fever, rabies, *Bacillus Calmette–Guérin* (BCG), and typhoid vaccine. Seasonal influenza vaccines for injection are generally killed virus vaccines and are allowed; however, intranasal influenza vaccines (eg, FluMist®) are live attenuated vaccines and are not allowed.
27. Has untreated active HBV.

Note: Antiviral therapy for HBV must be given for at least 3 months prior to first dose of study drug, and HBV viral load must be less than 100 IU/mL prior to first dose of study drug. Those on active HBV therapy with viral loads under 100 IU/mL should stay on the same therapy throughout study treatment. HBsAg, HBsAb, anti-HBe, anti-HBc and HBV DNA must be measured at baseline and during the study. Those subjects who are anti-HBc (+) and negative for HBsAg and HBV DNA do not require HBV prophylaxis, but need monitoring with HBsAg, HBsAb, anti-HBe, anti-HBc, and HBV DNA

28. HCV-positive subjects received a prior NS5A-containing regimen.
29. Has received a live vaccine within 30 days of planned start of study therapy (Cycle 1, Day 1). Note: The killed virus vaccines used for seasonal influenza vaccines for injection are allowed; however intranasal influenza vaccines (e.g., FluMist®) are live attenuated vaccines and are not allowed.
30. Subjects with a history of significant or unstable cardiac disease are excluded due to the hemolytic anemia associated with RBV. Subjects with proven coronary artery disease or angina.

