31. For Arm B subjects with HCV GT1a and have resistance polymorphisms are excluded if they have a CrCl of less than 50 mL/min.
32. Has received prior first-line therapy within 14 days of first dose of study medication.
33. Has a history or current evidence of any condition, therapy, or laboratory abnormality that might confound the results of the trial, interfere with the subject's participation for

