## 5.2 Trial Treatments

The treatment to be used in this trial are outlined in Table 3, Table 4, and Table 5. Please see prescribing information for Zepatier and RBV.

Table 3 Trial Treatments

Drug	Dose/Potency	Dose Frequency	Route of Administration	Regimen/Treatment Period	Use
Pembrolizumab	200 mg	Q3W	IV infusion	Day 1 of each 3-week cycle	Experimental
Zepatier	Tablet: 50 mg elbasvir and 100 mg grazoprevir	qday	PO	Daily See Table 4	Experimental
RBV	Capsule: 200 mg See Table 5	qday	PO	Daily	Experimental

Abbreviations: IV = intravenous; PO = oral; Q3W = every 3 weeks; qday = once daily; RBV = ribavirin.

The duration of Zepatier is dependent upon HCV GTs and presence or absence of resistance polymorphisms. Please see Table 4.

Table 4 Zepatier Trial Treatment Duration With or Without Cirrhosis

Patient Population	Treatment	Duration
GT1a: treatment-naïve without baseline NS5A polymorphisms 	Zepatier	12 weeks
GT1a: Treatment-naïve or PegIFN/RBV-experienced  or with baseline NS5A polymorphisms 	Zepatier + RBV 	16 weeks
GT1b: Treatment-naïve or PegIFN/RBV-experienced 	Zepatier	12 weeks
GT1a  or GT1b: PegIFN/RBV/PI-experienced 	Zepatier + RBV 	12 weeks
GT4: Treatment-Naïve	Zepatier	12 weeks
GT4: PegIFN/RBV-experienced 	Zepatier + RBV 	16 weeks

Abbreviations: GT = genotype; NS5A = non-structural protein 5A; PegIFN = pegylated interferon; RBV = ribavirin.

1. Patients who have failed treatment with PegIFN + RBV.
2. NS5A RAVs at amino acid positions 28, 30, 31, or 93. See Section 2.1 Testing prior to the initiation of therapy, subsection NS5A resistance testing in HCV GT1a-infected patients.
3. For patients with CrCl >50 mL per minute, the recommended dosage of RBV is weight-based (<66 kg = 800 mg per day, 66 to 80 kg = 1000 mg per day, 81 to 105 kg = 1200 mg per day, >105 kg = 1400 mg per day) administered in 2 divided doses with food. For patients with CrCl ≤50 mL per minute, including patients receiving hemodialysis, refer to the RBV tablet prescribing information for the correct RBV dosage.
4. The optimal Zepatier-based treatment regimen and duration of therapy for PegIFN/RBV/PI-experienced GT1a-infected patients with 1 or more baseline NS5A RAVs at positions 28, 30, 31, and 93 has not been established.
5. Patients who have failed treatment with PegIFN + RBV + HCV NS3/4A protease inhibitor (PI): boceprevir, simeprevir, or telaprevir.

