# Proprietary Information of MD Anderson

Protocol # 2016-0251

Date: February 24, 2020

46

Each Zepatier tablet contains 50 mg elbasvir and 100 mg grazoprevir, is beige, oval-shaped, film-coated, debossed with “770” on one side and plain on the other. The tablets are packaged into a carton (NDC 0006-3074-02) containing two (2) 14-count child-resistant dose packs for a total of 28 tablets.

Store Zepatier in the original blister package until use to protect from moisture. Store Zepatier at 20°C to 25°C (68°F to 77°F); excursions permitted between 15°C to 30°C (between 59°F to 86°F) [see USP Controlled Room Temperature].

In subjects with CrCl greater than 50 mL per minute, RBV will be administered twice a day (BID) PO (in RBV containing arms) at a total daily dose of 800 mg to 1400 mg based on subject weight on Day 1 (Table 5). RBV will be used for 12 to 16 weeks.

Table 5 Recommended Dosing for RBV in Combination Therapy for Subjects with CrCl Greater Than 50 mL Per Minute.

Body Weight in kg (lbs)	RBV Dose	Ribavirin capsules
<66 (<144)	800 mg/day	2 × 200 mg capsules A.M. 2 × 200 mg capsules P.M.
66-80 (145-177)	1000 mg/day	2 × 200 mg capsules A.M. 3 × 200 mg capsules P.M.
81-105 (178-231)	1200/mg day	3 × 200 mg capsules A.M. 3 × 200 mg capsules P.M.
>105 (>231)	1400 mg day	3 × 200 mg capsules A.M. 4 × 200 mg capsules P.M.

Abbreviations: A.M. = ante meridian; P.M. = post meridian; RBV = ribavirin.

Trial Treatment should begin within 3 days of allocation/assignment. However, every effort should be made to begin trial treatment on the day of allocation (ie, Cycle 1 Day 1).

The investigator shall take responsibility for and shall take all steps to maintain appropriate records and ensure appropriate supply, storage, handling, distribution and usage of trial treatments in accordance with the protocol and any applicable laws and regulations.

All trial treatments will be administered on an out-patient basis.

All products indicated in Table 3 will be provided centrally by Merck or locally by the trial site, subsidiary or designee, depending on local country operational or regulatory requirements.

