### **5.2.1.5 RBV Dose Modification (Escalation/Titration/Other)**

If Zepatier is administered with RBV refer to the RBV prescribing information for a description of RBV-associated adverse reactions. Monotherapy RBV for HCV is not permitted in this trial.

The primary toxicity of RBV is hemolytic anemia, which was observed in approximately 10% of RBV/Intron A-treated subjects in clinical trials. While this study does not include Intron A treatment hemolytic anemia surveillance is still warranted. The anemia associated with RBV capsules occurs within 1 to 2 weeks of initiation of therapy. Because the initial drop in

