# Proprietary Information of MD Anderson

Protocol # 2016-0251

Date: February 24, 2020

63

hemoglobin may be significant, it is advised that hemoglobin or hematocrit be obtained before the start of treatment and at Week 2 and Week 4 of therapy, or more frequently if clinically indicated. Subjects should then be followed as clinically appropriate. Fatal and nonfatal myocardial infarctions have been reported in patients with anemia caused by RBV. Subjects should be assessed for underlying cardiac disease before initiation of RBV therapy. Subjects with pre-existing cardiac disease should have electrocardiograms (ECGs) administered before treatment, and should be appropriately monitored during therapy. If there is any deterioration of cardiovascular status, therapy should be suspended or discontinued. Because cardiac disease may be worsened by drug-induced anemia, patients with a history of significant or unstable cardiac disease should not use RBV.

RBV should not be used in subjects with CrCl less than 50 mL/min. Subjects with impaired renal function and those over the age of 50 should be carefully monitored with respect to development of anemia.

If severe AEs or laboratory abnormalities develop during the study, RBV can be modified based on the recommended guidelines provided in Table 8.

For subjects with a history of stable cardiovascular disease, a permanent dose reduction is required if the hemoglobin decreases by greater than or equal to 2 g/dL during any 4-week period. In addition, for these cardiac history patients, if the hemoglobin remains less than 12 g/dL after 4 weeks on a reduced dose, the patient should discontinue combination therapy. It is recommended that a patient whose hemoglobin level falls below 10 g/dL have his/her RBV dose modified or discontinued per Table 9.

Subjects exhibiting the following conditions should be closely monitored and may require dose reduction or discontinuation of RBV therapy. Refer to the prescribing information:

- Hemolytic anemia may occur with a significant initial drop in hemoglobin
- Pancreatitis
- Pulmonary infiltrates or pulmonary function impairment
- New or worsening ophthalmologic disorders
- Concomitant administration of azathioprine
- Severe decreases in neutrophil and platelet counts and hematologic, endocrine and hepatic abnormalities
- Dental/periodontal disorders with combination therapy

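### The haemoglobin entry floor of 9.0 g/dL lies below the 10 g/dL level at which ribavirin reduction is recommended, so an Arm B subject without cardiac history can start full-dose ribavirin inside the reduction band

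*Combined protocol and SAP*

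**What the plan says.** **Entry.** Inclusion criterion 19 and Table 2 (section 5.1.2) set one haemoglobin floor for all subjects: at least 9.0 g/dL, or 5.6 mmol/L. The entry carries a superscript a.

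**Starting dose.** Table 4 assigns ribavirin to several Arm B groups by genotype, polymorphism and prior treatment. For creatinine clearance above 50 mL/min, its footnote says "the recommended dosage of RBV is weight-based", and the text with Table 5 gives it "at a total daily dose of 800 mg to 1400 mg based on subject weight on Day 1". Neither mentions haemoglobin.

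**Management on treatment.** Section 5.2.1.5 introduces Table 8 this way: "If severe AEs or laboratory abnormalities develop during the study, RBV can be modified based on the recommended guidelines provided in Table 8". For subjects without cardiac history, Table 8 reduces ribavirin at 8.5 to <10 g/dL and stops therapy below 8.5 g/dL. The same section adds: "It is recommended that a patient whose hemoglobin level falls below 10 g/dL have his/her RBV dose modified or discontinued per Table 9". (Table 9 holds the dose steps; the thresholds are in Table 8.)

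**Timing and monitoring.** "The anemia associated with RBV capsules occurs within 1 to 2 weeks of initiation of therapy". Because the early fall can be large, "it is advised that hemoglobin or hematocrit be obtained before the start of treatment and at Week 2 and Week 4 of therapy". Section 7.1.3.1 likewise recommends those tests. The flow chart marks the complete blood count at screening and then from Cycle 2, and its footnote sets it once per 3-week cycle.

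**Ribavirin-related entry criteria.** Exclusion 30: "Subjects with a history of significant or unstable cardiac disease are excluded due to the hemolytic anemia associated with RBV". Exclusion 31: "For Arm B subjects with HCV GT1a and have resistance polymorphisms are excluded if they have a CrCl of less than 50 mL/min". Neither concerns haemoglobin.

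**The concern.** The protocol treats haemoglobin below 10 g/dL as a reason to give less ribavirin, yet on its visible text it lets a subject begin the full dose at that level. Section 5.2.1.5 calls haemolytic anaemia the drug's main toxicity and reports myocardial infarctions, some fatal, in patients made anaemic by it. A subject entering at 9.0 g/dL has 0.5 g/dL in hand before the stop limit.

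The plan already restricts entry for ribavirin risk on cardiac and renal grounds. The measure that ribavirin lowers directly has no matching criterion in the text that can be seen. The stake is the safety of individual subjects; no sample size, power or error rate is involved.

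**Working it through.** **1. The plan's own figure.** Table 2 gives the floor in two units. With 16.114 g/mmol as the conversion factor (an outside constant), 9.0 × 10 / 16.114 = 5.585, which rounds to the printed 5.6 mmol/L. The floor is internally consistent.

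**2. Overlap of entry range and reduction band.**
- Eligible: 9.0 g/dL and above (Table 2).
- Reduction band, no cardiac history: 8.5 to <10 g/dL (Table 8).
- Overlap: 9.0 to <10 g/dL, width 10 − 9.0 = 1.0 g/dL.

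The row for stable cardiac history triggers reduction by a change in haemoglobin, so it is not part of this comparison.

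**3. Distance to the stop limit of 8.5 g/dL.**
- At the floor: 9.0 − 8.5 = 0.5 g/dL.
- At the top of the overlap: 10 − 8.5 = 1.5 g/dL (not reached).
- With a floor of 10 g/dL: overlap zero, smallest distance 10 − 8.5 = 1.5 g/dL.
- In Table 2's other unit, 10 × 5.6 / 9.0 = 6.2 mmol/L.

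**4. First scheduled blood count after starting.** If ribavirin starts on Cycle 1 Day 1, the next scheduled count belongs to Cycle 2, about 21 days later. Even if the 3-day visit window and the 72-hour pre-dose allowance are both used in full, it comes at 21 − 3 − 3 = 15 days. The anaemia is expected within 7 to 14 days. Only the advised Week 2 test falls at the end of that window.

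**5. How many subjects.** The documents do not give this number, so two assumptions are needed.
- Assumption 1: all 15 Arm B subjects are treatment-naive GT1a, and ribavirin is given only for baseline NS5A polymorphisms, at the US prevalence in section 7.1.4.2.2: 37/309 = 0.1197. Expected ribavirin subjects: 15 × 0.1197 = 1.80.
- Assumption 2 (not from the documents): a share f of ribavirin subjects enters at 9.0 to <10 g/dL.
- Chance of at least one: 1 − (1 − 0.1197 f)^15.

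| f | Expected affected (1.80 × f) | Chance of at least one | Bound if all 15 had ribavirin (15 × f) |
|---|---|---|---|
| 5% | 0.09 | 9% | 0.75 |
| 10% | 0.18 | 17% | 1.5 |
| 20% | 0.36 | 30% | 3.0 |

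Assumption 1 can err either way. Under Table 4, treatment-naive GT1b and GT4 subjects receive no ribavirin. If only half of Arm B were GT1a, the share in the Phase III treatment-naive trial described in section 4.2.1.4, and the rest were treatment-naive GT1b or GT4, the expected count would halve to about 0.05, 0.09 or 0.18. Prior treatment failure raises it, because Table 4 adds ribavirin for several experienced groups. The right-hand column is a bound, not a forecast.

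**The case against.** **The thresholds serve different purposes.** Table 8 and the 10 g/dL sentence concern haemoglobin that falls, or abnormalities that arise, during treatment. A reader might infer that the protocol contradicts itself or that such a subject would breach a dosing rule on Day 1. The documents do not support that: no baseline haemoglobin rule for ribavirin is visible, and Table 8 is worded as a recommended guideline. The mismatch remains.

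**A stricter rule may exist.** A reader might also infer that the plan has no ribavirin haemoglobin floor at all. That cannot be established. The text of footnote a was not available for this review, and Table 2's abbreviations define erythropoietin, which the visible table never uses. Sections 5.2 and 5.2.1.1 defer ribavirin details to the prescribing information, and section 5.5.3 applies the label's contraindications. This objection stands and makes the point conditional.

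**Safeguards exist.** Section 7.1.3.1 requires laboratory results to be reviewed and judged acceptable before trial treatment is given, and Table 3 lists ribavirin as a trial treatment. Exclusions 19 and 33 let the investigator refuse entry for a laboratory abnormality, exclusion 30 addresses cardiac disease, and erythropoietin is allowed. If the advised Week 2 test is done, the monitoring gap largely closes. These measures lower the risk, but none supplies a haemoglobin number for starting ribavirin, and Table 2 tells the investigator that 9.0 g/dL is adequate.

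**The 10 g/dL figure proves little.** The documents give no expected size of fall, so they cannot show that 1.5 g/dL is enough or that 0.5 g/dL is too little. A subject starting at exactly 10.0 enters the band after any fall. That is fair; the figure is chosen because it is the protocol's own action level.

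**Other remedies exclude nobody.** A mandatory Week 2 test alone would detect a fall sooner but leave the overlap. Starting at Table 9's first reduced step would depart from the weight-based dose the protocol recommends.

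**Conclusion.** The point holds as a minor mismatch of thresholds. On the visible text, a subject without cardiac history who is assigned ribavirin can start full dose at 9.0 to <10 g/dL, a level at which the protocol recommends reduction once treatment is under way, with 0.5 to <1.5 g/dL left before the stop limit.

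The effect is very small: probably none or one of about 15 Arm B subjects. That headcount depends on an all-GT1a, treatment-naive arm and on an assumed share of low-haemoglobin entrants. Treatment-naive GT1b or GT4 subjects would lower it and prior treatment failure would raise it. The overlap and the margins depend on neither assumption, but they do depend on footnote a and the ribavirin label not being stricter.

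This is a cheap improvement to consider, not a demonstrated defect.

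**What to change.** In Table 2, add a line requiring haemoglobin of at least 10 g/dL (about 6.2 mmol/L) to start ribavirin for subjects assigned it under Table 4. Keep 9.0 g/dL for everyone else. State that a subject below 10 g/dL may be rescreened, as section 7.1.6.2 already permits. Make the Week 2 and Week 4 haemoglobin tests mandatory for ribavirin subjects and enter them in the flow chart. If footnote a or the ribavirin label already sets a stricter floor, print that floor in Table 2 instead.

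**Cost.** The change is one line in Table 2 and one in the flow chart. Ribavirin subjects have one or two extra blood counts; the liver-panel footnote already calls for weekly sampling in the first two cycles, so the same draws could serve. Possibly one Arm B subject is delayed or excluded. Since section 3.0 describes Arm A as HCV-negative, an excluded subject would have no other arm and would lose on-trial pembrolizumab and Zepatier, although section 4.3.2 describes pembrolizumab as an approved second-line therapy in this disease.

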# Proprietary Information of MD Anderson

Protocol # 2016-0251

Date: February 24, 2020

64

Table 8 Dose Reduction Rules for RBV

Laboratory Parameters	Reduce RBV if	Discontinue Therapy if
HGB without a history of cardiac disease	8.5 to <10 g/dl	< 8.5 g/dl
HGB with a history of stable cardiac disease	<2 g/dL decrease in hemoglobin during any 4-week period during treatment	<8.5 g/dL or <12 g/dL after 4 weeks of dose reduction

Abbreviations: HGB = hemoglobin; RBV = ribavirin

Table 9 Dose Modifications for RBV

Body Weight on Day 1	FDD (mg/day)	1st RBV Reduction		2nd RBV Reduction		3rd RBV Reduction	
		Dose (mg/day)	Number of 200 mg Capsules	Dose (mg/day)	Number of 200 mg Capsules	Dose (mg/day)	Number of 200 mg Capsules
51-65 kg (112-114 lb)	800	600	1 in AM/ 2 in PM	400	1 in AM/ 2 in PM	200	1 in AM/ 2 in PM
66-80 kg (145-177 lb)	1000	800	2 in AM/ 2 in PM	600	1 in AM/ 2 in PM	400	1 in AM/ 2 in PM
81-105 kg (178-231 lb)	1200	1000	2 in AM/ 3 in PM	800	2 in AM/ 2 in PM	600	1 in AM/ 2 in PM
105-125 kg (232-275 lb)	1400	1000	2 in AM/ 3 in PM	800	2 in AM/ 2 in PM	600	1 in AM/ 2 in PM

Abbreviations: AM = ante meridian; FDD = full daily dose; PM = post meridian; RBV = ribavirin

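### Ribavirin dose-reduction tables are wrong as printed: three of 12 capsule counts in Table 9 do not give the stated dose, and the cardiac hemoglobin trigger in Table 8 reverses the text

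*Combined protocol and SAP*

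**What the plan says.** Section 5.2.1.5 names hemolytic anemia as the main toxicity of RBV and gives two working tables.

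- **Table 8** says when to reduce or stop. Without cardiac history, RBV is reduced at hemoglobin 8.5 to <10 g/dL and stopped below 8.5 g/dL. With stable cardiac disease, the printed reduction trigger is "<2 g/dL decrease in hemoglobin during any 4-week period during treatment".
- **The text of Section 5.2.1.5** states the cardiac rule separately: "a permanent dose reduction is required if the hemoglobin decreases by greater than or equal to 2 g/dL during any 4-week period".
- **Table 9** says how far to reduce. For each weight band it gives three successive doses in mg/day, each with an entry under "Number of 200 mg Capsules". The text says that a patient whose hemoglobin falls below 10 g/dL should "have his/her RBV dose modified or discontinued per Table 9".
- **Table 5** (Section 5.2) gives the full starting doses with capsule counts; its lowest band, for example, is "2 × 200 mg capsules A.M. 2 × 200 mg capsules P.M" for 800 mg/day.

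Exclusion 30 (Section 5.1.3) narrows the cardiac group: "Subjects with a history of significant or unstable cardiac disease are excluded due to the hemolytic anemia associated with RBV". Its next sentence adds proven coronary artery disease or angina.

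**The concern.** Each Table 9 cell gives the same instruction twice, once in milligrams and once in capsules, so the two must agree. In three cells they do not, and each time the capsule count gives more drug than the milligram figure. The capsule count is what an outpatient handles: under Section 7.1.1.14, subjects record home doses in a diary. A subject prescribed 400 mg who takes the printed count takes 600 mg, which also meets the protocol's overdose definition for agents other than pembrolizumab (Section 7.2.2).

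The Table 8 trigger, read alone, calls for a reduction after a 1 g/dL fall but not after a 3 g/dL fall. The effect carries forward, because the cardiac stopping rule of <12 g/dL applies only after four weeks on a reduced dose. A site that misses the reduction also loses that safeguard and is left with the stop at <8.5 g/dL. Section 5.2.1.5 itself notes fatal and nonfatal myocardial infarctions in patients with RBV anemia.

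**Working it through.** **Table 9.** Inputs are the printed dose and the printed morning and evening counts in each cell, with a capsule strength of 200 mg. The check is: daily dose = (AM + PM capsules) × 200 mg.

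| Band | Reduction | Printed mg/day | Printed AM + PM | Capsules × 200 mg | Result |
|---|---|---|---|---|---|
| 51-65 kg (full dose 800) | 1st | 600 | 1 + 2 | 600 | agrees |
| | 2nd | 400 | 1 + 2 | 600 | +200 mg (1.5×) |
| | 3rd | 200 | 1 + 2 | 600 | +400 mg (3×) |
| 66-80 kg (full dose 1000) | 1st | 800 | 2 + 2 | 800 | agrees |
| | 2nd | 600 | 1 + 2 | 600 | agrees |
| | 3rd | 400 | 1 + 2 | 600 | +200 mg (1.5×) |
| 81-105 kg (full dose 1200) | 1st | 1000 | 2 + 3 | 1000 | agrees |
| | 2nd | 800 | 2 + 2 | 800 | agrees |
| | 3rd | 600 | 1 + 2 | 600 | agrees |
| 105-125 kg (full dose 1400) | 1st | 1000 | 2 + 3 | 1000 | agrees |
| | 2nd | 800 | 2 + 2 | 800 | agrees |
| | 3rd | 600 | 1 + 2 | 600 | agrees |

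Nine cells agree and three do not. Followed by capsule count, the sequences are:

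- 51-65 kg: 800, 600, 600, 600 mg/day, against the printed 800, 600, 400, 200.
- 66-80 kg: 1000, 800, 600, 600 mg/day, against the printed 1000, 800, 600, 400.

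**Which column is wrong.** The same check on Table 5 gives (2+2)×200 = 800, (2+3)×200 = 1000, (3+3)×200 = 1200 and (3+4)×200 = 1400, so all four rows agree. The mg/day column in Table 9 falls at every step, as a reduction schedule should. The capsule counts are therefore the likely misprint. The same whole entry stands in all three wrong cells, which looks like copied table content rather than a reading error.

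**Weight range.** The first row reads "51-65 kg (112-114 lb". But 51 kg × 2.2046 = 112.4 lb, 65 kg × 2.2046 = 143.3 lb, and 114 lb is only 51.7 kg. Table 5 bounds this band at <144 lb, and the next row of Table 9 is "66-80 kg (145-177 lb". The upper limit should be 144 lb.

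**Table 8.** The table and the text concern the same group and the same four-week window.

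| Fall in hemoglobin over 4 weeks | Table 8 as printed (<2 g/dL) | Section 5.2.1.5 text (≥2 g/dL) |
|---|---|---|
| 1 g/dL | reduce | no reduction required |
| 3 g/dL | no reduction | permanent reduction required |

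No fall satisfies both rules.

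**The case against.** The Table 9 arithmetic is not in dispute. The case on the other side concerns certainty, harm and reach.

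- **The Table 8 symbol may be a reading error.** This cannot be excluded from the text alone. Other ≥ signs came through intact (Table 2, Table 12), which supports the printed reading without proving it. The point stands as a reason to check the source page.
- **The text already gives the right cardiac rule, in mandatory terms, just before the table, and the table's version is clinically absurd.** This is true and lowers the chance of harm. But the same text also points sites to Table 8 as guidance for modifying RBV, so the conflict should not remain.
- **Entry at low hemoglobin does not reach the wrong cells.** Table 2 (Section 5.1.2) admits subjects at ≥9.0 g/dL, inside the 8.5 to <10 g/dL reduction band. That triggers only a first reduction, and all four first-reduction cells are correct. This stands: low entry hemoglobin makes reductions foreseeable, but the error appears only at a second or third step within a 12 to 16 week course.
- **Other safeguards exist.** The intended mg/day is printed beside each count, Table 8 stops therapy below 8.5 g/dL, and several sections refer to the prescribing information. These help, but none corrects the counts, and a general reference does not override a specific table that the text tells sites to use.
- **Few subjects are exposed.** The number on RBV is not given. It could be 0 to about 15, all of Arm B. For scale, Section 7.1.4.2.2 reports NS5A polymorphisms in 12% (37/309) of US GT1a subjects. If all 15 were treatment-naive GT1a and only those with polymorphisms received RBV (an assumption), 0.12 × 15 = 1.8, or about 2. Prior HCV treatment would change this.

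These points bear on likelihood and urgency. They do not make the entries correct.

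**Conclusion.** The tables are wrong as written. Three of 12 capsule counts in Table 9 give 600 mg/day where 400, 200 and 400 mg/day are stated, too high by 200, 400 and 200 mg/day. This rests on the printed figures and multiplication only, and confidence is high. The printed Table 8 cardiac trigger reverses the text rule, subject to confirming one symbol on the source page.

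The scope is narrow. Table 9 matters for Arm B subjects whose regimen includes RBV, at the second or third reduction in the 51-65 kg band or the third in the 66-80 kg band. Table 8 matters for those with stable cardiac disease who pass exclusion 30. Sample size, DLT counting and endpoint definitions are unaffected. It still needs correcting, because these are live dosing instructions, every capsule error runs toward too much of a hemolytic drug, and nothing elsewhere in the protocol repairs Table 9.

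**What to change.** Change five entries:

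1. Table 9, 51-65 kg, second reduction (400 mg): two capsules, for example one morning and one evening.
2. Table 9, 51-65 kg, third reduction (200 mg): one capsule.
3. Table 9, 66-80 kg, third reduction (400 mg): two capsules, for example one morning and one evening.
4. Table 9, first weight band: 112-144 lb.
5. Table 8, stable cardiac disease: reduce at a fall of ≥2 g/dL in any four-week period, matching Section 5.2.1.5.

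Check each entry against the source page and the RBV labelling first, then issue the amendment and a dosing clarification to the site. The cost is a text correction, with no new procedures, data or analyses.
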